5.4 Inclusion/Exclusion Criteria

Inclusion/Exclusion Criteria: To be eligible for the study, participants will be 18 or older with a history of mild TBI (DoD/VA criteria⁶⁶ as determined by trained, experienced staff via interview and medical record review via comprehensive evaluation process within PNS Clinic⁶⁵) with current symptoms complaints (operationally defined as at least two symptoms on the NSI endorsed at the 'moderate' level or a total score on the NSI greater than 25. At least 93.5 percent of a sample of over 50,000 individuals with mild TBI within VA reported at least two NSI symptoms at a moderate level of severity or higher.⁶⁷ In addition, eligible participants must speak and read English, not have a history of moderate to severe TBI, not have a self-reported diagnosis of psychosis or be actively suicidal. Finally, potential subjects who report prior experience with Concussion Coach will also be excluded. We will attempt to recruit women and minorities to the extent possible. Our experience suggests that approximately 4% female and 30% ethnic minority will likely participate; they agree to participate in research at about the same rate as male and non-minority participants. Subjects who meet the inclusion/exclusion criteria and who agree to participate in the research study will sign an informed consent.

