- Neurobehavioral Symptom Inventory (NSI) is a 22-item questionnaire developed to evaluate post-concussion symptoms following mild TBI.⁵² It is used throughout the VA system of care to assess complaints associated with identified concussion. Patients are asked to rate each symptom on a scale of 0-4 (none, mild, moderate, severe, and very severe) with three different types of symptoms: affective/psychological/stress, somatic/physical, and cognitive reflecting three factors. The total score will be used in primary analyses. It is our primary outcome of interest because the civilian literature on interventions for mild TBI has focused (and found effects) on symptom-based measures.^{41 53} Our own pilot data suggests that educational interventions have a significant impact on this measure.
- mBIAS is a 5-item measure of atypical symptoms. It is associated with symptom exaggeration following mild TBI (Cooper et al., 2011).
- Brief Symptom Inventory 18 (BSI 18) is a self-report measure with 18 items designed to measure psychological distress. It can be completed in approximately 4 minutes and is well-suited for helping measure symptom change due to treatment. It has good psychometric properties and has been used in the population of interest. It measures three primary dimensions: Somatization, Depression, and Anxiety, as well as a Global Severity Index (GSI). The GSI will be used in primary analyses as a measure of overall psychological distress. The Posttraumatic Stress Disorder Checklist (PCL-5) is a 20-item, self-rating scale that provides a quick and accurate measure of PTSD symptoms. Each item corresponds to current diagnostic criteria of PTSD, and each symptom is rated in terms of frequency and severity (Weathers, Huska, & Keane, 1991).Participant use of Concussion Coach will be collected electronically, including total time spent using the app as well as each component.

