All data will be combined into a study database. The integrity of the database will be managed by our database manager. Analyses will be conducted by the statistician ([name]) and the PI ([name]).

Data Analysis Plan: An intention-to-treat (ITT) analysis will be performed, that is analysis will be based on the groups to which participants are randomized regardless of whether they receive or adhere to the assigned intervention. This will allow us to test the effects of assigning TBI Coach in practice, separate from assessing effects of adherence and/or loss to follow-up. Those who are lost to follow-up and therefore are missing outcome measures (T2 assessments) will be included in separate comparison analyses that utilize multiple imputations of the missing data.

For each primary outcome and other measures consisting of multiple items, a summation score will be produced for each subject. Summary of each variable by intervention group will be cross-tabulated. The time spent on TBI Coach and its specific components on the average will also be tabulated. All primary outcomes will be analyzed as continuous variables. Exploratory bivariate plots will be used to investigate possible nonlinear relationships between baseline/covariates and each follow up outcome variable. In separate statistical models proposed, we will control for demographics and other covariates including the baseline values of the outcome under investigation. Where appropriate, nonlinear regression model will be utilized (e.g., generalized additive model).

Hypothesis 1 (Primary Hypothesis): Patients randomized to receive TBI Coach for 3 months will have (a) lower post-concussive symptom severity and (b) lower psychological distress, compared to patients randomized to a no intervention control group, after adjusting for baseline severity and other potential confounders.

Analysis: The two intervention groups (TBI Coach = 1; Control = 0) will be compared on each outcome (a) and (b) in separate regression models that include the group variable and control for the outcome at baseline and other potential confounders. A significant positive estimated coefficient of the group variable will indicate positive TBI Coach's effects on the outcome, with the standardized value of the coefficient as the standardized effect size.

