be performed using the Mplus statistical application which offers alternatives that do not require the regular assumption of symmetric, normal distributions for parameter estimates. Bayesian estimation method with diffuse priors will be used with appropriate posterior simulation schemes based in Markov Chain Monte Carlo (MCMC) methods. One advantage of the MCMC estimation process is that it provides accurate tests of mediated effects for small samples; e.g. by simply taking the product of the two coefficients alpha and beta for every draw and compute its standard deviation across all draws to obtain standard errors of mediated effect. Also, unlike the normal-based ML confidence interval, inference will rely on Bayesian credibility interval based on the percentiles of the posterior, which easily allows for a strongly skewed distribution alphabeta product⁷⁴

Hypothesis 4: More time spent on (a) TBI Coach use, and (b) specific interactive components of TBI Coach (i.e., the "tools" section) will be associated with lower PCS symptom severity after adjusting for baseline PCS values and potential confounders.

Analysis: A regression model of PCS will be performed on the TBI Coach sample only, separately for (a) TBI coach use, and (b) each interactive component as the main predictor. First the PCS baseline score, demographics and other potential confounders will be included in the base model. Then a full model with addition of the time score for one TBI Coach aspect at a time will be fitted. Appropriate transformation (e.g. log) of all time variables will be done as suggested by their general distribution; a significant negative coefficient of the time variable will confirm a negative association between time spent on that component and symptom severity. Standardized coefficient estimates as well as R-sq estimates will be obtained so that all TBI Coach aspect-specific models can be compared on the relative strengths of the aspect-outcome relationships.

As an extension, secondary analysis will be performed on the TBI Coach components that show strong relationship in the expected direction. Each time spent (as a dependent variable) will be regressed on the predictors in the base model to identify both positive and negative contributory factors to the specific component usage.

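### The sign in the Hypothesis 1 decision rule is reversed: with the app coded 1 and higher scores meaning worse, it reads significant harm as benefit and misses real benefit

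*Combined protocol and SAP*

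**What the plan says.** Section 5.6 (Data Analysis) calls the app TBI Coach. Hypothesis 1 there predicts that patients given the app will have "a) lower post-concussive symptom severity and (b) lower psychological distress" than controls, and Aim 1 in section 3.0 says the same.

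The analysis paragraph specifies the comparison: "The two intervention groups (TBI Coach = 1; Control = 0) will be compared on each outcome", in separate regression models that adjust for the baseline value of the outcome and other potential confounders. The reading rule follows: "A significant positive estimated coefficient of the group variable will indicate positive TBI Coach's effects on the outcome". The same sentence makes the standardized coefficient the effect size.

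On scoring, section 5.5 says of the NSI: "Patients are asked to rate each symptom on a scale of 0-4 (none, mild, moderate, severe, and very severe", and "The total score will be used in primary analyses". Psychological distress is measured by the BSI-18 Global Severity Index. Section 5.6 builds each multi-item outcome as a sum and treats it as continuous.

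For Hypothesis 4, which uses the same symptom outcome, the stated rule is that "a significant negative coefficient of the time variable will confirm a negative association between time spent on that component and symptom severity".

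**The concern.** With the app coded 1, the group coefficient is the adjusted mean score under the app minus that under control. If higher scores are worse, a positive coefficient means that the app arm did worse. The rule attaches the word positive, in the sense of favourable, to the sign that shows harm.

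The primary conclusion is at stake. No other rule in the plan says what result supports Hypothesis 1. The standardized coefficient is also the headline effect size, so its direction is mislabelled too.

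Direction is a live question in this trial. The Introduction (section 2.0) says that drawing attention to the TBI label can itself increase symptom reporting, and the app delivers TBI education and repeated symptom self-rating. Section 5.1 says that the principal investigator and three co-investigators helped develop the app, and section 5.6 has the principal investigator share in the analyses. A direction fixed clearly in advance protects the result.

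**Working it through.** **1. Direction of the scale.** NSI items run from 0 (none) to 4 (very severe) and are summed, so a higher total is worse. Section 5.4 agrees: one of the two ways to qualify as currently symptomatic is "a total score on the NSI greater than 25". The direction of the BSI-18 items is not spelled out. It follows from the index being used as a measure of overall distress and from Hypothesis 1 seeking lower distress. The available text contains no reversed score and no outcome defined as baseline minus follow-up.

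**2. Sign of the coefficient.** The model is: follow-up score = a + b × group + c × baseline score + other covariates, with group = 1 for the app. Then b = adjusted mean (app) − adjusted mean (control). Hypothesis 1 predicts b < 0. The rule asks for b > 0.

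**3. Comparison with Hypothesis 4.** On the same symptom score, Hypothesis 4 links a negative coefficient to lower severity. That matches step 2 and shows that the scale is not reversed elsewhere in the plan.

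**4. The plan's own sample-size figures.**
- Expected N: (20 × 33 + 150) × 0.60 × 0.80 = 388.8, which agrees with the stated 388.
- F-test for an added R-squared of 0.05 from 2 terms, with 10 covariates at R-squared 0.20: f² = 0.05 / (1 − 0.20 − 0.05) = 0.0667; noncentrality = N × f²; degrees of freedom 2 and N − 13. The minimum N is 148 for 80% power (0.8006) and 194 for 90% power (0.9016), both as stated.

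The F-test ignores sign, so these figures do not depend on the rule.

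**5. What the rule does if followed literally.** The documents give no SD and no target difference for Hypothesis 1, so effects are assumed in SD units. Equal arms of 194 and a two-sided 0.05 test are also assumed. Without covariate adjustment, SE = √(2/194) = 0.1015 SD. For a true benefit of size d:
- P(significant negative) = Φ(d/SE − 1.96)
- P(significant positive) = 1 − Φ(d/SE + 1.96)

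| True effect (SD) | Real benefit declared, rule as written | Equal harm declared a benefit, rule as written | Real benefit declared, sign corrected |
|---|---|---|---|
| 0.20 | 4.3 × 10⁻⁵ | 0.504 | 0.504 |
| 0.25 | 4.9 × 10⁻⁶ | 0.692 | 0.692 |
| 0.30 | 4.5 × 10⁻⁷ | 0.840 | 0.840 |
| 0.50 | 2.9 × 10⁻¹² | 0.998 | 0.998 |

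With covariates explaining a share R² of the variance, SE = √(4/388 × (1 − R²)). For a benefit of 0.25 SD:
- R² = 0.36 (assumed): SE = 0.081, P(significant negative) = 0.868, P(significant positive) = 2 × 10⁻⁷.
- R² = 0.20 (the plan's power-calculation figure): SE = 0.091, 0.25/0.091 = 2.75, P(significant negative) ≈ 0.79, P(significant positive) ≈ 1.2 × 10⁻⁶.

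**6. Simulation.** In 4,000 simulated trials with 194 per arm, baseline R² of 0.20 and baseline adjustment:
- a true benefit of 0.30 SD gave a significant positive coefficient in none and a significant negative one in 91.4%;
- a true harm of 0.30 SD gave 91.2% significant positive and none significant negative;
- no effect gave 2.5% significant positive and 2.3% significant negative.

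**The case against.** The strongest reply is that this is a slip which no competent analyst would follow. Hypothesis 1 stands just above the rule and fixes the direction as lower. Nothing says that a significant negative coefficient will be disregarded. The plan also tabulates each variable by arm, so the raw direction would be visible. The test, the model and the sample size are unchanged. All of this is fair, and it means that the near-zero probabilities describe literal obedience to the rule and are not a loss built into the design. It does not make the sentence right: a pre-specified criterion should not depend on readers silently reversing it.

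A second reply is that a positive effect on the outcome may mean only that the score goes up. That is arithmetically true, but the rule would then describe the direction that Hypothesis 1 does not predict, and the plan would contain no criterion for success. The sentence would still need rewriting.

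Three smaller points stand. The R² of 0.36 in the illustration is higher than the plan's 0.20, which moves the figures but not the conclusion. Table 1 also lists the PCL-5 under psychological distress, so the corrected rule should cover every distress score that is analysed. The plan does not state whether the test of the Hypothesis 1 coefficient is one- or two-sided, so adding two-sided is a new specification, though one that fits the non-directional F-test at 0.05.

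**Conclusion.** The rule is wrong as written. With the app coded 1, unreversed severity scores and a hypothesis of lower scores, benefit is a negative coefficient, and the plan names a positive one. Taken literally, over true effects of 0.20 to 0.50 SD, the rule would declare a real benefit with probability between 4 × 10⁻⁵ and 3 × 10⁻¹², and would label an equal harm a benefit with probability 0.50 to 0.998.

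Those probabilities rest on assumed effect sizes, equal arms, 388 analysed participants and a two-sided 0.05 test. The sign error itself rests on none of them. It would disappear only if the outcomes were reverse-scored or defined as improvement, and the plan does neither. Because this is the only stated criterion for the primary hypothesis, it must be corrected before outcomes are compared by arm.

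**What to change.** Replace the rule in the Hypothesis 1 analysis paragraph of section 5.6 with wording such as:

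> A significant negative coefficient of the group variable (app minus control, two-sided p < 0.05) indicates lower post-concussion symptom severity or psychological distress with TBI Coach. A significant positive coefficient indicates a worse outcome with TBI Coach.

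State that the standardized coefficient carries the same sign convention, and that higher values are worse on every score analysed under Hypothesis 1. This brings Hypothesis 1 into line with Hypothesis 4.

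The cost is one or two sentences. Design, data collection, model and sample size do not change. The abstract reports enrolment at 93% of the goal, so the correction should be made and dated now, before follow-up outcomes are analysed by arm.

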Q2: What are the moderators and mediators of the effectiveness of Concussion Coach?

- (a) Is comfort with technology related to efficacy of Concussion Coach?
- (b) Is perceived social support related to efficacy of Concussion Coach?

Q3: Does use of Concussion Coach (a) increase Veterans' knowledge about TBI and change Veterans' attribution of symptoms from mild TBI to less "pathological" explanations (e.g., stress, post-deployment re-adjustment, or other causes), (b) increase Veterans' self-efficacy in coping with symptoms?

More broadly, are the effects of Concussion Coach on PCS and psychological distress mediated through change (from T1 to T2) in Veterans' perceptions and knowledge of the illness and in self-efficacy?

Q4: What aspects of Concussion Coach are most associated with positive outcomes among recipients of Concussion Coach? Is more frequent use of specific components of Concussion Coach associated with greater improvement, relative to other components?

Q5: What are the factors associated with use of Concussion Coach or with deriving benefit from use of Concussion Coach that can be used to inform future modifications of the application and wide scale implementation?

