Hypothesis 2: The effects of TBI Coach on PCS (and psychological distress) will be greater for Veterans who have (a) greater comfort with technology at baseline than for those who are less comfortable; (b) greater social support at baseline than for those with less social support.

Analysis: Two separate tests of moderated effects of TBI Coach will be performed with respect to each outcome. Each regression model in H1 (one per outcome) will be extended by adding a 2-way interaction term (between intervention and (a) eHealth Literacy Scale and (b) Social Support score; one at a time (i.e. two different moderation models per outcome). A significant coefficient of an interaction term will indicate presence of interactive effects. A co-plot using model fitted values will also be produced to further investigate the nature of any significant interaction.

Hypothesis 3: If TBI Coach improves Veterans' (a) knowledge about TBI and attribution of symptoms and/or (b) self-efficacy in coping with symptoms, Veterans will have less PCS and Psychological Distress.

Analysis: Single-mediator models⁷³ will test the indirect effects of the group variable (TBI Coach) on each outcome (separately) with respect to mediating variables: (a) knowledge and attribution, and (b) self-efficacy. Preliminary regression analyses will test whether (1) TBI Coach substantially changes the mediating variable, and (2) the mediating variable changes the outcome. Next, we will proceed to a full mediation model with simultaneous estimation of both direct and indirect effects of TBI Coach on the outcome. The mediated effect will be estimated as a product of the two path coefficients alpha and beta in the indirect pathway. The distribution of the product of coefficients is non-normal and this has implications for statistical inference as well as power calculation (see section on sample size justification). Therefore, the analysis will

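### Hypothesis 3 tests the two mediators only in separate models, so the joint mediated effect asked about in Q3 is not estimated and credit cannot be divided between them

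*Combined protocol and SAP*

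**What the plan says.** Section 5.6 (Hypothesis 3, Analysis) uses single-mediator models that "will test the indirect effects of the group variable (TBI Coach) on each outcome (separately) with respect to mediating variables". The mediators are "a) knowledge and attribution, and (b) self-efficacy".

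Two preliminary regressions check whether "TBI Coach substantially changes the mediating variable, and (2) the mediating variable changes the outcome". The plan then fits a "full mediation model with simultaneous estimation of both direct and indirect effects of TBI Coach on the outcome". What is estimated together there is the app's direct and indirect effect, not the two mediators.

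On estimation: "The mediated effect will be estimated as a product of the two path coefficients alpha and beta in the indirect pathway". On inference: "inference will rely on Bayesian credibility interval based on the percentiles of the posterior".

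For covariates, the general part of the Data Analysis Plan says "we will control for demographics and other covariates including the baseline values of the outcome under investigation". The other mediator is not named.

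In section 2.0, the broader part of Q3 asks whether the app's effects on symptoms and distress run through change in Veterans' "perceptions and knowledge of the illness and in self-efficacy". Section 5.6 defines no joint or total indirect effect that would answer this.

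**The concern.** Knowledge and attribution, and self-efficacy, are both patient questionnaires given at the same assessments (section 5.5, Table 1). The app contains both teaching material and coping skills, so it may plausibly move both. If the two are also correlated within arm, the mediator-to-outcome path in a single-mediator model absorbs part of the effect of the omitted mediator.

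The preliminary regressions do not guard against this. A mediator that the app moves, and that merely correlates with an active one, can pass both.

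Two things are at stake. Q3's joint question has no planned estimate. And a positive single-mediator result could be read as evidence for that mediator in particular, when the model cannot separate it from the other.

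**Working it through.** **1. The plan's own figures.** Section 5.6 gives N=388, both paths 0.14, SD 0.5 for predictor and mediator, squared predictor-mediator correlation 0.3, error SD 0.2 and alpha 0.05 (taken as two-sided).

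- N: (20 × 33 + 150) × 0.6 × 0.8 = 388.8.
- Residual mediator variance: 0.25 × (1 − 0.3) = 0.175, so residual SD 0.418.
- Sobel Z = ab / √[a² × 0.04/(388 × 0.175) + b² × 0.175/(388 × 0.25)] with a = b = 0.14. This is 0.0196 / √(0.00001155 + 0.00003536) = 2.86.
- Power = 0.816, against 0.82 stated. The plan's figure reproduces, but it is power for one mediator taken alone.

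**2. What a single-mediator model estimates.** Let the app move both mediators by a. Let mediator 2 affect the outcome with coefficient b and mediator 1 have no effect. Let the residuals have equal SDs and within-arm correlation r.

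- Mediator 1 alone: its outcome path is r × b, so its indirect effect is a × r × b. The true value is 0.
- Mediator 2 alone: its indirect effect is a × b, which is correct.
- Sum of the two: a × b × (1 + r), against a true total of a × b. The overstatement is r, so 20% to 50% for r from 0.2 to 0.5.

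Example with a = 0.14, b = 0.39, r = 0.3: 0.14 × 0.3 × 0.39 = 0.0164 for the inert mediator, and 0.14 × 0.39 = 0.0546 for the active one. The sum is 0.0710, and 0.0710/0.0546 = 1.30.

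**3. How often the inert mediator is declared a pathway.** This was simulated at N=388 with 1:1 allocation and a 95% percentile interval for alpha × beta from approximate diffuse-prior draws. The plan does not state the interval level, so 95% is an assumption. The correlation r is also an assumption. The paths 0.14 and 0.39 are the small and medium values that section 5.6 lists.

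| Setting | r | Single-mediator model | Both mediators in one model |
|---|---|---|---|
| Paths 0.14/0.39 | 0.2 | 22% | 3% to 4% |
| Paths 0.14/0.39 | 0.3 | 38% | 3% to 4% |
| Paths 0.14/0.39 | 0.5 | 73% | 3% to 4% |
| Plan's power inputs (0.14/0.14) | 0 | 4.9% | 4.7% |
| Plan's power inputs | 0.3 | 34% | 4.4% |
| Plan's power inputs | 0.5 | 67% | 3.3% |

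Separate runs of the 0.14/0.39 setting agree within a few points (for example 42% at r = 0.3).

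**4. Conditions.** At r = 0 there is no excess, as the table shows. If the app does not move the inert mediator, the single-model rate is at most 4.8% for r up to 0.7 with the plan's inputs. Both conditions are therefore needed.

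**5. Cost in power.** With the plan's inputs, power for the real mediator is about 0.91 in its single model and 0.89 to 0.91 in the two-mediator model.

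**The case against.** **Causal order.** The strongest objection is that the rates above need not be errors. If knowledge acts on symptoms by raising self-efficacy, the single-mediator effect of knowledge is a legitimate total effect through knowledge. Simulating that chain (app moves both by 0.14, knowledge to self-efficacy 0.3 or 0.5, self-efficacy to outcome 0.39), the single-mediator model detects knowledge in about 45% and 74% of trials. The true effects are 0.14 × 0.3 × 0.39 = 0.016 and 0.14 × 0.5 × 0.39 = 0.027. The specific effect of knowledge in a parallel model averages about zero and is significant in only 3% to 4%. This objection stands: a parallel model should not be the sole basis for claims about mechanism, and the assumed order must be stated. The total indirect effect through both mediators is the same under either order in a linear model, so the joint model still answers Q3.

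**Shared self-report.** The outcomes are self-reported at the same visits too. If an unmeasured factor supplies 10% or 20% of the residual variance of both mediators and the outcome, the two-mediator model itself declares the inert mediator a pathway in 32% or 71% of trials (single-mediator: 53% and 79%). This also stands. The 3% to 4% holds only without such confounding.

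**Readings that go too far.** A reader might infer that the plan double-counts the joint pathway. It does not: nowhere does it add the two estimates. A reader might also infer that Hypothesis 3 is meant to choose which part of the app to modify. The documents tie future modification to the qualitative aim, and Hypothesis 3 is worded so that either mediator, or both, may be involved.

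**Standing.** Aim 2 describes mediation as something to explore, and Table 1 calls these measures potential mediators. That limits the weight of the point. Even so, Hypothesis 3 is a stated hypothesis and section 5.6 calls the mediation model the most demanding in sample size.

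**Conclusion.** The point holds in a limited form. Hypothesis 3 leaves Q3's joint indirect effect unestimated, and its separate models cannot divide credit between two correlated mediators.

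The rate of roughly 22% to 73%, against 3% to 4% in a joint model, rests on five assumptions: the app moves both mediators; their within-arm correlation is 0.2 to 0.5; one has no effect of its own; the correlation is not itself causal; and nothing unmeasured confounds the mediators with the outcome. The documents neither establish nor exclude these, so the figures show what could happen and do not predict an error rate for this trial. The 20% to 50% overstatement applies only if someone adds the two estimates.

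This is an inexpensive improvement to a mediation analysis that ranks below the primary hypothesis. The test of Hypothesis 1 is untouched.

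**What to change.** Add to the Hypothesis 3 analysis in section 5.6 one pre-specified two-mediator model per outcome in Mplus, containing both mediators and their residual covariance. Then:

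- Report the total indirect effect as the answer to Q3, together with each specific indirect effect, using the Bayesian credibility intervals already planned.
- State the assumed causal order of the mediators: parallel, or knowledge acting through self-efficacy.
- State the assumption of no unmeasured confounding between mediators and outcome.
- Keep the single-mediator models, but do not attribute an effect to one mediator rather than the other from those models alone.

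This needs a few lines of text and code, no new data and no new software. The downside is somewhat wider intervals for the specific effects when the mediators are correlated. Recruitment was still under way at this version of the protocol, so the change could be made before analysis.
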